# **Time-to-Event Efficacy Endpoints**

The following time-to-event endpoints will be analyzed:

- Pain freedom through 4 hours post-dose
- Pain freedom through 8 hours post-dose
- MBS freedom through 8 hours post-dose for subjects with MBS reported at on-study migraine attack onset
- Pain relief through 4 hours post-dose
- Pain relief through 8 hours post-dose
- Nausea freedom through 8 hours post-dose for subjects with nausea present at on-study migraine attack onset
- Phonophobia freedom through 8 hours post-dose for subjects with phonophobia present at on-study migraine attack onset
- Photophobia freedom through 8 hours post-dose for subjects with photophobia present at onstudy migraine attack onset
- Return to normal function through 8 hours post-dose for subjects with functional disability at on-study migraine attack onset.

Analyses are based on non-missing, post-dose efficacy data relevant to each endpoint.

For a given time-to-event endpoint, subjects are considered to have an event through X hours (X = 4 or 8) if the first post-dose eDiary finding date/time defining response is (1) at or before the upper bound of the X-hour analysis window in minutes (see Table 5), and (2) is before the imputed rescue medication start date/time, if not missing (see Section 7.3).

Otherwise, subjects who do not have an event through X hours will be censored at the earliest of the following: (1) upper bound of the X-hour analysis window + 1 minute; (2) time from the study drug start date/time to the imputed rescue medication start date/time, if the time is at or before the upper bound of the X-hour analysis window in minutes; (3) time from the study drug start date/time to the last non-missing finding date/time defining the endpoint, if the time was before the lower bound of X-hour analysis window in minutes.

For each endpoint listed above, time to event will be assessed by treatment group as follows:

- KM plot and table using the following time intervals post-dose: 0 to 15, >15 to 30, > 30 to 45, > 45 to 60, > 60 to 90, > 90 to 120, > 120 to 180, > 180 to 240, > 240 to 360, > 360 to 495, and > 495 minutes. The KM plot will display the percentage of subjects with the event on the y-axis versus time in minutes on the x-axis. See Section 7.1.1.1 for KM plot and table attributes.
- Time-to-event distribution table (minutes), including a log-rank p-value (BHV-3500 versus placebo).

See Section 7.1.1.1 for time-to-event plot and table attributes.

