# 2.3 Objective Estimands

An estimand is the target of estimation to address the scientific question of interest posed by a study objective. The four attributes of an estimand include the population of interest, endpoint of interest, specification of how intercurrent events are reflected in the scientific question of interest, and the population-level summary for the endpoint.

For all objectives, the population of interest is defined through appropriate inclusion/exclusion criteria to reflect the targeted patient population for approval. Refer to the protocol for inclusion/exclusion criteria.

Intercurrent events are those that occur after treatment initiation and either preclude observation of the endpoint or affect its interpretation. Rescue medication taken at or before the time point of interest defining the endpoint will be considered an intercurrent event. This event is relevant to all efficacy endpoints, except the secondary endpoint of rescue medication use within 24 hours post-dose.

For efficacy objectives, intercurrent events will be handled with a composite strategy, i.e., the occurrence of the intercurrent event will be integrated as a component of the endpoint. See Section 6.3.1 for additional details.

For safety and outcomes research objectives, intercurrent events will be handled with a treatment policy strategy, i.e., the occurrence of the intercurrent event will be considered irrelevant, such that all observed values of the endpoint of interest will be used regardless of rescue medication use.

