# 6.3.1 Principal Analysis Methods of Handling Missing Data and Intercurrent Events

Methods of handling missing data in principal analyses of binary efficacy endpoints are defined as follows:

- Non-Completer = Failure (NC=F): Subjects with missing data at a single time point will be classified as failures. This missing data imputation method will be applied to endpoints based on data from a single time point (e.g., co-primary endpoints at 2 hours post-dose).
- Non-Completer With Missing Data at More Than 1 Time Point = Failure (NC1=F): Subjects with missing data at > 1 time point post-dose in a specified time period will be classified as failures. This missing data imputation method will be applied to endpoints that are based on data from multiple time points (e.g., secondary endpoint of sustained pain freedom from 2 to 24 hours post-dose).
- Non-Completer = Missing (NC=M): Subjects with missing data at a single time point will be excluded from the analysis. This missing data exclusion method will be applied to endpoints based on data from a single time point (e.g., co-primary endpoints at 2 hours post-dose).

The intercurrent event of rescue medication use will be handled using Rescue Medication = Failure (RM=F), i.e., subjects who take rescue medication will be classified as failures for all efficacy evaluations that are reported at or after taking rescue medication, i.e., (1) rescue medication start date/time  $\leq$  eDiary finding date/time if start time is not missing, or (2) rescue medication start date  $\leq$  eDiary finding date if start time is missing; see Sections 6.2.5.2 and 7.3). This method will apply to all efficacy analyses, except the secondary endpoint of rescue medication use within 24 hours post-dose.

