### **Complete Cases Over Time: Sensitivity Analyses**

Response rates corresponding to efficacy outcomes over time will also be presented using complete cases for each of the following efficacy endpoints: pain freedom, MBS freedom, pain relief, nausea freedom, phonophobia freedom, photophobia freedom, and return to normal function. Percentages for response rates will also be shown with exact Clopper-Pearson 98.3% CIs.

In these sensitivity analyses, subjects who are missing data in a post-dose time point analysis window will be excluded at that time point (NC=M). Results for the co-primary endpoints of

pain freedom and MBS freedom at 2 hours post-dose will be the same as those for the complete cases sensitivity analyses (see Sections 6.3.3.1 and 6.3.3.2).

For MBS freedom, the following conventions will be applied: (1) first, subjects whose MBS at on-study migraine attack onset is missing will be classified as failures; (2) next, the RM=F method of handling intervening rescue medication use will be applied; (3) finally, subjects with missing data in the analysis window will be excluded.

For all other endpoints, the RM=F method of handling intervening rescue medication use will be applied first, and then subjects with missing data in the analysis window will be excluded.

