### 7.1.1.1 Time-to-Event Tables and Plots

Time-to-event endpoints will be summarized with KM tables displaying the following at each time interval:

- Number of subjects at risk, defined as those who did not have the event just prior to the start of the interval and who were not censored prior to the interval
- Number of subjects with events, defined as those who had the event for the first time during the interval
- Number of subjects censored, defined as those who did not have the event and whose censoring date/time is in the interval
- Cumulative probability of having the event with lower and upper CI limits, based on the KM product limit method.

Time-to-event endpoints will also be summarized with corresponding KM plots displaying 100 times the cumulative probability of having the event on the y-axis and time on the x-axis, including the number of subjects at risk at each time point below the x-axis.

Time-to-event distributions of endpoints will be summarized with the following descriptive statistics: number and percentage of subjects with events; number and percentage of subjects censored in or before the last time interval; number and percentage of subjects censored in the last time interval; median time to event with CI using the method of Brookmeyer and Crowley.

CI levels will be 98.3% for efficacy endpoints and 95% for all other endpoints.

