## 7.3 Derived Dates

Derived dates are defined as follows:

- Study drug start date/time: Earliest study medication date and time from the eDiary Migraine Report or Study Medication Intake Report (see Section 7.6.3.1). This date is used to define analysis periods.
  - o eDiary Migraine Report
    - If the subject answered "yes" to taking study medication mistakenly already, then the following conventions will be applied depending when drug was reported taken:
      - Today: study drug start date will be set to the finding date, and the study drug start time will be set to the time of study medication taken, if available.
      - Yesterday: study drug start date will be set to the finding date -1 day, and study drug start time will be set to the time of study medication taken, if available.
      - Other: study drug start date will be set to the date of study medication taken, if available.
    - Otherwise, if the subject answered "no" to taking study medication mistakenly already and answered "yes" to confirming having taken study medication, then the study drug start date/time will be set to the finding date/time.
  - o Study Medication Intake Report: Study medication date/time.
- Rescue medication start date/time: Earliest rescue medication date/time (see Section 6.2.5.2). Missing time is considered to be earlier than non-missing time on the same date.
- Imputed rescue medication start date/time: This will be used only for time-to-event efficacy analyses in Section 6.3.5.2, and not for time to rescue medication use analyses in Section 6.3.4.3.
  - o If the rescue medication start date and time are both not missing, then the imputed rescue medication start date/time will be set to the rescue medication start date/time.
  - If the rescue medication start time is missing and the rescue medication start date is
    equal to the study drug start date, then the imputed rescue medication start date/time will
    be set to the study drug start date/time.
  - Otherwise, if the rescue medication start time is missing and the rescue medication start date is equal to a post-dose eDiary finding date with non-missing efficacy data, then the imputed rescue medication start date/time will be set to the first eDiary finding date/time corresponding to non-missing efficacy data.
  - Otherwise, if the rescue medication start time is missing and rescue medication start date is equal to the study drug start date + 1 day, then the imputed rescue medication start

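### The time-to-event efficacy analyses censor non-responders at rescue medication, although SAP 6.3.1 counts rescue as failure in all efficacy analyses but one, so the Kaplan-Meier curves read too high

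*SAP*

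**What the plan says.** SAP 2.3 defines rescue at or before the time point of interest as the intercurrent event for all efficacy endpoints except rescue use within 24 hours. It then states: "For efficacy objectives, intercurrent events will be handled with a composite strategy". SAP 6.3.1 makes this operational as Rescue Medication = Failure (RM=F): "This method will apply to all efficacy analyses, except the secondary endpoint of rescue medication use within 24 hours post-dose".

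In SAP 6.3.5.2, the outcomes over time use RM=F, and so do the complete-case sensitivity analyses: for endpoints other than MBS freedom, "the RM=F method of handling intervening rescue medication use will be applied first, and then subjects with missing data" are excluded; for MBS freedom, a missing MBS at onset is classed as failure before RM=F is applied.

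The time-to-event endpoints in the same section follow another rule. A response is an event only if it "is before the imputed rescue medication start date/time, if not missing". A subject without an event is censored at the earliest of three times, the second being the "time from the study drug start date/time to the imputed rescue medication start date/time, if the time is at or before the upper bound" for that window. The output is described thus: "The KM plot will display the percentage of subjects with the event on the" y-axis. SAP 7.1.1.1 uses the product-limit method and counts as at risk only subjects without the event "who were not censored prior to the interval".

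**The concern.** The time-to-event analyses are the only part of SAP 6.3.5.2 that departs from RM=F. No exception is named, and Table 3 (SAP 2.3.3) gives them no estimand of their own.

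The rule also conflicts with its own event definition. After rescue a subject cannot have the event, so the subject is a known non-responder for the rest of the window. Censoring instead treats the outcome as unknown, and one minus Kaplan-Meier gives that subject the later response rate of subjects still at risk. Two consequences follow.

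- The curve exceeds the share of subjects who respond before rescue whenever a response follows a rescue censoring. This needs no dependence between rescue and response.
- Protocol 5.4.1 permits rescue after 2 hours to subjects without relief, or whose migraine returns. The censoring is therefore informative, and the curve does not cleanly estimate a no-rescue scenario either.

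At stake is the reading of descriptive onset curves at 4 and 8 hours. Because other headache medication is prohibited for the first 2 hours, the distortion falls mainly between 2 and 8 hours.

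**Working it through.** **Plan figures.** The documents give no figure for these analyses. The only usable inputs are the 2-hour rates in SAP 5. With 380 per group and a two-sided alpha of 0.0167, those rates reproduce the stated power: 90.1% for pain freedom, 90.3% for MBS freedom, 81.4% jointly. Rescue rates and response rates after 2 hours are not given, so every such value below is an assumption.

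**Exact small case.** Of 100 subjects, 20 respond at 120 min, 30 take rescue at 125 min without a response, 20 respond at 240 min and 30 never respond.

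- SAP rule: 50 subjects are at risk at 240 min, so 1 − (80/100)(30/50) = 52%.
- Rescue as failure: (20 + 20)/100 = 40%, the true share responding before rescue.

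**Closed form.** Let p be the proportion responding by 2 h (22% active, 12% placebo), l the hourly response hazard and r the hourly rescue hazard after 2 h, and T the time after 2 h. T is 2.25 h for the 4-hour window bound and 6.25 h for the 8-hour bound (SAP Table 5).

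- SAP rule: 1 − (1 − p)·exp(−lT)
- Rescue as failure: p + (1 − p)·[l/(l + r)]·[1 − exp(−(l + r)T)]

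Example at T = 6.25:

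- Active, l = 0.08, r = 0.05. SAP rule: 1 − 0.78·exp(−0.5) = 52.7%. Rescue as failure: 0.22 + 0.78·(0.08/0.13)·[1 − exp(−0.8125)] = 48.7%. Excess 4.0 points.
- Placebo, l = 0.06, r = 0.10. SAP rule: 1 − 0.88·exp(−0.375) = 39.5%. Rescue as failure: 0.12 + 0.88·(0.06/0.16)·[1 − exp(−1)] = 32.9%. Excess 6.7 points before rounding.
- Treatment difference: 13.2 points under the SAP rule, 15.8 with rescue as failure.

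At T = 2.25 the excess is 0.7 and 1.1 points, and the difference is 11.7 against 12.2.

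**Range.** The grid takes l from 0.04, 0.06, 0.08, 0.10 and 0.15 per hour with active at least equal to placebo (15 pairs), and r from 0.04, 0.05, 0.08, 0.10 and 0.12 with placebo above active (10 pairs): 150 combinations.

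| Time | Excess, active | Excess, placebo |
|---|---|---|
| 4 h 15 min | 0.3 to 2.2 points | 0.4 to 2.9 points |
| 8 h 15 min | 1.9 to 10.5 points | 2.6 to 13.7 points |

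At 8 h 15 min the treatment difference is off by −9.0 to +4.9 points. Placebo has the larger excess in 79% of combinations and active in 21%. One reversal: active 0.15/0.08 and placebo 0.04/0.10 (l/r) give excesses of 8.7 and 4.8 points, and a difference of 38.0 instead of 34.1.

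**Diary times.** In a simulation of 1,000,000 subjects per arm with the example hazards and responses recorded only at 3, 4, 6 and 8 h, the 8-hour values are 51.8% against 47.0% on active and 38.6% against 30.8% on placebo. The result does not depend on the continuous-time formula.

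**Untimed rescue.** Under SAP 7.3, if the rescue time is missing and the date is "equal to the study drug start date, then the imputed rescue medication start date/time will" be set to the dosing date and time. The subject is censored at time 0, before any event can occur. SAP 6.3.1 compares dates for the same subject and counts a failure in the denominator. If a share q of an arm is affected, a response share p reads p/(1 − q). For assumed q of 1% to 10%, 22% reads 22.2% to 24.4% and 12% reads 12.1% to 13.3%.

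**The case against.** The strongest defence has four parts.

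- **Scope.** SAP 6.3.1 is headed as principal methods and introduces its missing-data rules for binary endpoints. RM=F makes evaluations at or after rescue failures; the time-to-event event rule respects that and is silent only on the risk set. This does not remove the conflict: the RM=F paragraph sets its own scope, all efficacy analyses with one exception, and SAP 2.3 is not limited to binary endpoints.
- **Intent.** The revision history shows that this algorithm was changed to use an imputed rescue time, and SAP 7.3 reserves that variable for these analyses. The rule may be deliberate. No reason is given, and the exception is not stated where it belongs.
- **Consequence.** The p-values are descriptive and outside the hierarchy (SAP 6.1.2, 6.3.5), and RM=F response rates are planned at every time point. This stands and limits the importance. Those rates describe status at a time point, however, not first response by that time, so they do not correct the curves.
- **Size.** The 22% and 12% are pain-free rates at 2 hours, whereas the curve counts first response at any time, so its 2-hour value should be higher. Assumed starts of 30% and 18% reduce the example's excess from 4.0 and 6.7 to 3.6 and 6.2 points. The grid minima reflect its floor of 0.04 per hour: with l = 0.04 and r = 0.02 the excess is 1.0 and 1.1 points, and with r = 0.01 about 0.5. This stands. The figures are illustrations, and the excess could be small if rescue is rare.

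**Conclusion.** The concern holds. Censoring at rescue contradicts SAP 2.3 and 6.3.1, and the product-limit curve does not show the percentage of subjects with the event as SAP 6.3.5.2 defines that event. The direction for each curve is certain: never too low, and too high once a rescue censoring is followed by a response in another subject.

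The size is not known from the documents. Under the assumed constant hazards it is several points at 8 hours and at most 2.9 points at 4 hours; lower rescue rates give less. No claim is made that the rule favours active treatment. Alpha, power, the co-primary tests and the secondary hierarchy are untouched. The correction should be made because it is simple and because two conflicting rules for rescue would otherwise stand in one report.

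**What to change.** In SAP 6.3.5.2, replace the second censoring rule. A subject who takes rescue before responding stays in the risk set as a non-responder and is censored at the upper bound of the X-hour window plus 1 minute. Limit the third rule (last non-missing finding) to subjects who have not taken rescue, so that it cannot move rescued subjects earlier. This also resolves the time-0 censoring of untimed same-day rescue.

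The cost is SAP wording and one derivation rule. Kaplan-Meier tables, plots and log-rank tests remain, and the curves fall by the excess described above. Without dropout the rule returns the rescue-as-failure proportion exactly (47.0% and 30.8% in the simulation). With dropout hazards of 1% to 5% per hour it reads 0.1 to 0.6 points low at 8 hours; at 5% it gives 46.4% against 46.9% on active and 30.2% against 30.8% on placebo. The shortfall is about 1 point if rescue after the diary stops also counts as failure.

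Cumulative incidence with rescue as a competing event handles dropout better, but costs more because it replaces the Kaplan-Meier tables and the log-rank test.

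If the sponsor prefers to censor at rescue, SAP 6.3.1 should name these analyses as an exception. They should be labelled a sensitivity analysis with their own hypothetical estimand, and the y-axis description should be changed accordingly.

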# 7.6.3.2 Migraine Characteristics

The following migraine characteristics will be collected at migraine attack onset in the eDiary Migraine Report and post-dose from 15 minutes through 48 hours (e.g., 15, 30, 45, 60, and 90 minutes; 2, 3, 4, 6, 8, 24 and 48 hours) in the eDiary Post-Dose Migraine Report:

- Pain level (none, mild, moderate, severe)
- MBS (nausea, phonophobia, photophobia) in the Migraine Report only
- Nausea status (present, absent)
- Nausea level (none, mild, moderate, severe)
- Phonophobia status (present, absent)
- Phonophobia level (none, mild, moderate, severe)
- Photophobia status (present, absent)
- Photophobia level (none, mild, moderate, severe)
- Functional disability level (normal, mildly impaired, severely impaired, requires bedrest)
- Aura (yes, no) in the Migraine Report only.

The eDiary will allow subjects to report one result per time point per migraine characteristics parameter.

In general, if subjects answered "no" to taking study medication mistakenly already, had current pain level of moderate or severe, and did not use other headache medications, then the eDiary Migraine Report will collect all parameters listed above.

Otherwise, if subjects answered "yes" to taking study medication mistakenly already, then the eDiary Migraine Report will not collect the following parameters: most bothersome symptom, current pain level, nausea status, phonophobia status, and photophobia status. Instead, if the subject provided the time of study medication taken, then the eDiary Migraine Report will collect nausea level, phonophobia level, photophobia level, pain level and functional disability level at the time study drug was taken. Thus, for these subjects at on-study migraine attack onset, a symptom status (nausea, phonophobia, photophobia) of absent is defined as a level of none, and present is defined as a level of mild, moderate, or severe.

Windows for post-dose efficacy measurements (15, 30, 45, 60, 90 minutes; 2, 3, 4, 6, 8, 24, and 48 hours) will be automatically assigned by the eDiary as shown in Table 5.

Table 5: eDiary Automated Efficacy Analysis Windows

Post-Dose Evaluation	Analysis-Specified Interval	Target Time
15 minutes	10 to 20 minutes	Study medication start time + 15 minutes
30 minutes	25 to 35 minutes	Study medication start time + 30 minutes
45 minutes	40 to 50 minutes	Study medication start time + 45 minutes
60 minutes	55 to 65 minutes	Study medication start time + 60 minutes

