90 minutes	85 to 95 minutes	Study medication start time + 90 minutes
2 hours	1 hour 45 minutes to 2 hours 15	Study medication start time + 2 hours
3 hours	2 hours 45 minutes to 3 hours 15	Study medication start time + 3 hours
4 hours	3 hours 45 minutes to 4 hours 15	Study medication start time + 4 hours
6 hours	5 hours 45 minutes to 6 hours 15	Study medication start time + 6 hours
8 hours	7 hours 45 minutes to 8 hours 15	Study medication start time + 8 hours
24 hours	23 to 25 hours	Study medication start time + 24 hours
48 hours	47 to 49 hours	Study medication start time + 48 hours

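### In the SAP 6.3.5.2 time-to-event analyses, a diary entry made after the 4- or 8-hour window can decide when a subject is censored inside it

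*SAP*

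**What the plan says.** SAP 6.3.5.2 (Time-to-Event Efficacy Endpoints) lists nine exploratory endpoints. Two run through 4 hours (pain freedom, pain relief). Seven run through 8 hours (the same two, MBS freedom, freedom from each of the three symptoms, and return to normal function).

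A response is an event only if its diary time is no later than the upper end of the X-hour window and precedes rescue. A subject without an event is censored at the earliest of:

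1. the "upper bound of the X-hour analysis window + 1 minute";
2. the time to "the imputed rescue medication start date/time, if the time is at or before the upper bound of the X-hour analysis window";
3. the time to "the last non-missing finding date/time defining the endpoint, if the time was before the lower bound of X-hour analysis window".

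On which data enter, the section says only: "Analyses are based on non-missing, post-dose efficacy data relevant to each endpoint".

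Table 5 in SAP 7.6.3.2 gives the windows: "3 hours 45 minutes to 4 hours 15" for 4 hours and "7 hours 45 minutes to 8 hours 15" for 8 hours. The same pain, symptom and function items are also collected at 24 and 48 hours. SAP 7.1.1.1 keeps a subject in the risk set for every interval that starts before the event or the censoring time.

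**The concern.** Limb (3) evidently exists to end follow-up when diary observation ends. The event rule and limb (2) both carry a time limit. Limb (3) carries none on which finding is the last one. A 24- or 48-hour entry therefore makes the last finding later than the window's lower bound, and the limb no longer applies. For the two 4-hour endpoints a 6- or 8-hour entry does the same.

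The subject then stays at risk through hours in which no event could have been recorded. Two subjects with identical data in the window get different censoring times because of what they did after it.

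The pattern is foreseeable. Protocol 5.4.1 asks subjects to keep making entries to 48 hours, and the quality-of-life and preference questionnaires fall due in the handheld at 24 hours. The SAP itself expects gaps at 3 to 8 hours: it tabulates missing time points (6.3.2) and has a rule for them in the sustained endpoints (6.3.4.5 to 6.3.4.8).

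At stake are the Kaplan-Meier curves, medians and log-rank p-values of nine planned analyses.

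**Working it through.** **1. Windows.** The 8-hour upper bound is 8 × 60 + 15 = 495 min, which reproduces the last Kaplan-Meier cut-point in SAP 6.3.5.2. The lower bound is 465 min. The 4-hour window is 225 to 255 min. The 24-hour window starts at 23 × 60 = 1380 min, beyond both lower bounds.

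**2. The rule applied to diary patterns** (no response in the window, no rescue). In-window means that limb (3) counts only findings up to the X-hour upper bound.

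| Entries | X | As written | In-window |
|---|---|---|---|
| to 2 h, nothing later | 8 | 120 min | 120 min |
| to 2 h, then 24 h | 8 | 496 min | 120 min |
| to 6 h, then 24 h | 8 | 496 min | 360 min |
| to 2 h, nothing later | 4 | 120 min | 120 min |
| to 2 h, then 24 h | 4 | 256 min | 120 min |

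The second subject stays at risk from 120 to 495 min, which is 375 min without ascertainment. It makes no difference whether the 24-hour entry shows pain. With rescue at 150 min, limb (2) censors at 150 under either reading.

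**3. Formula.** Let F2 and F8 be cumulative response by 2 and 8 h, and q the share of 2-hour non-responders who are silent at 3 to 8 h but make a later entry. If gaps are unrelated to response, the rule as written loses q × (F8 − F2) of the events and keeps those subjects at risk, so the 8-hour estimate is F8 − q × (F8 − F2). In-window censoring gives F8.

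**4. Numbers for pain freedom.** F2 = 22% (active) and 12% (placebo) come from SAP section 5; using these 2-hour rates as cumulative response is a simplification. F8 = 50% and 35% is an assumption, and so is q. F8 − F2 is 28 and 23 points. The simulation used 400,000 subjects per arm.

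| q | Active: formula (simulated) | Placebo: formula (simulated) | Difference by formula (true 15.0) |
|---|---|---|---|
| 2% | 49.4% (49.5%) | 34.5% (34.4%) | 14.9 |
| 5% | 48.6% (48.6%) | 33.9% (33.8%) | 14.75 |
| 10% | 47.2% (47.1%) | 32.7% (32.7%) | 14.5 |
| 20% | 44.4% (44.4%) | 30.4% (30.4%) | 14.0 |

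The shifts run from 0.02 × 23 = 0.46 to 0.20 × 28 = 5.6 points. In-window censoring returned 49.9% to 50.1% and 34.9% to 35.0%. With F8 of 55% and 40% instead, the largest shifts (q = 20%) would be 0.20 × 33 = 6.6 and 0.20 × 28 = 5.6 points.

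**5. Unequal gaps.** With q of 10% on active and 5% on placebo, the difference is 47.2 − 33.85 = 13.35 points. With 5% and 10% it is 48.6 − 32.7 = 15.9.

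**6. Informative gaps.** Let r be the 8-hour response among silent subjects. As written, the estimate is F8 − q(1 − F2)r. In-window, it is F2 + [F8 − F2 − q(1 − F2)r]/(1 − q). For active with q = 20%, q(1 − F2) = 0.20 × 0.78 = 0.156. The values of r are assumed; gaps unrelated to response correspond to r = 0.28/0.78 = 35.9%.

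- r = 10%: as written 0.50 − 0.0156 = 48.4%; in-window 0.22 + 0.2644/0.80 = 55.05%.
- r = 70%: as written 0.50 − 0.1092 = 39.1%; in-window 0.22 + 0.1708/0.80 = 43.35%.

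The true value is 50% in both cases.

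**The case against.** **The rule may already mean findings within X hours.** The endpoints are named as running through 4 or 8 hours, the data are said to be those relevant to each endpoint, and a 24-hour entry does not naturally define an 8-hour endpoint. On that reading the problem disappears. The reading is possible, but the text does not secure it. The event rule also speaks of findings that define response and still states its time limit separately, and the data sentence gives no limit. Two programmers could reasonably produce different curves.

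**The literal rule errs on the cautious side.** It resembles the SAP's principal convention of counting missing data as failure, and step 6 shows it closer to the truth than in-window censoring when silent subjects rarely respond. This stands. In-window censoring is unbiased only if gaps are non-informative. What does not stand is the rule as a form of that convention, because it treats a gap as non-response only when the subject happens to make a later entry.

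**The gaps would be visible elsewhere.** Response at each time point is reported with missing as failure and for complete cases (6.3.5.2), and missing pain data are tabulated (6.3.2). Those tables would reveal material gaps, but they show response at a time point, not cumulative response, and do not correct the curves.

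**The size is assumed.** This is correct: no gap rate and no 8-hour response rate is given.

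**Conclusion.** Read literally, limb (3) gives identical in-window data different censoring times according to entries made after the window. It affects non-responders without rescue in the window who have a gap reaching the X-hour window and a later entry. Relative to in-window censoring, and with gaps unrelated to response, the limb lowers 8-hour cumulative response by q × (F8 − F2): about 0.5 to 5.6 points for q of 2% to 20% with assumed 8-hour pain freedom of 50% and 35%. With equal gaps the arm difference shrinks slightly; with unequal gaps it can move either way.

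A reader might infer three stronger things that the documents do not support:

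- That the published curves are biased down overall. Limb (2) censors at rescue instead of counting failure, which can push the same curves up, so the net direction is not established.
- That in-window censoring recovers the truth. Step 6 shows that it does not when gaps are informative.
- That efficacy conclusions are at risk. SAP 6.1.2 and 6.3.5 make exploratory p-values descriptive and outside the hierarchy, and no co-primary or secondary test uses this rule.

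**What to change.** In SAP 6.3.5.2, restrict limb (3) to the latest non-missing endpoint finding dated no later than the X-hour upper bound (255 or 495 min after dosing). Censor there when that finding precedes the X-hour lower bound (225 or 465 min). Entries at 24 and 48 hours, and at 6 and 8 hours for the 4-hour endpoints, then no longer extend follow-up.

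Add that a subject with no finding up to that upper bound is censored at time 0. The mITT definition in SAP section 3 accepts efficacy data from any post-dose time, so such subjects can exist.

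The cost is one phrase and one sentence in the SAP, a condition in the program, and slightly fewer subjects at risk late in the curve. The change should be made before database lock.
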